6.4.3 Analysis of double-blind treatment Period D

Efficacy variables for the Period D are similar to those defined for Week 52, and will be summarized over the entire 104 weeks of randomized treatment.

Durability of effect will be assessed using descriptive and graphical presentations of efficacy variables over time. A summary of the number of patients who maintain desirable HbA1c levels at each time point in Period D will be generated. The same methods used to investigate the slopes of HbA1c after Week 24 in the Period C will be employed to compare the HbA1c slopes from Week 24 through Period D in the two treatment regimens. A repeated measures analysis may also be performed on change from baseline in HbA1c.

Safety variables for the long-term period are similar to those defined in Period C, and will be summarized over the entire 104 weeks of randomized treatment.

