Assessment of glycaemic parameters (based on results from central laboratory) will be done to determine if criteria for discontinuation are met during the period.

The patients will be instructed to monitor their blood glucose at least every second day. Hypoglycaemic events should be entered into the patient diary. The evaluation at each of the titration visits and final decision by the investigator on dose increase (or decrease) should take into account both the plasma glucose measurements made by the patients prior to visits and the investigator's measurements at the titration visits.

Maintenance treatment period (Visits 10-13)

After the titration period, the patient will return for visits to assess efficacy and safety of the treatment. At any time during the study, investigational product glipizide can be down-titrated to mitigate recurrent hypoglycaemic events at the discretion of the investigator, no up-titration is allowed. The patients will continue to monitor their blood glucose at least once a week. Hypoglycaemic events should be entered into the patient diary. Assessment of glycaemic parameters (based on results from central laboratory) will be done at each visit to determine if criteria for discontinuation are met during the period.

Randomized patients in the Titration or Maintenance treatment period who do not complete the entire study should complete the procedures described for Visit 13 (end of Period C).

Extension period (Period D) (Visits 14-17)

After 52 weeks, eligible patients will continue in the randomized extension treatment period with the same treatment given at the end of Period C. The patient will return for visits approximately every thirteenth week to assess efficacy and safety of the treatment. The patients will continue to monitor their blood glucose at least once a week. Hypoglycaemic events should be entered into the patient diary. At any time during the study, investigational product glipizide can be down-titrated to mitigate recurrent hypoglycaemic events at the discretion of the investigator, no up-titration is allowed. Assessment of glycaemic parameters (based on results from central laboratory) will be evaluated at Visit 14 to 16 to determine eligibility for discontinuation during the period. The patients will stop taking investigational product at the end of treatment visit, Visit 17.

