3.3.5 Discontinuation of patients from treatment or assessment

3.3.5.1 Criteria for discontinuation

Patients may be discontinued from study treatment and assessments at any time. Specific reasons for discontinuing a patient from this study are:

- 1. Voluntary discontinuation by the patient who is at any time free to discontinue his/her participation in the study, without prejudice to further treatment.
- 2. Safety reasons as judged by the investigator, AstraZeneca and/or Bristol-Myers Squibb Pharmacovigilance.
- 3. Severe non-compliance to protocol as judged by the investigator and/or AstraZeneca.
- 4. Incorrect enrolment or randomization, ie, the patient does not meet the required inclusion/exclusion criteria for the study.
- 5. Patient lost to follow-up (as defined by, unable to reach the patient after 3 documented phone calls, fax, e-mail, or attempts to contact him/her through patient

locator agencies (if allowed per national regulation) and having sent one letter by registered/certified mail; all should be documented in the patients medical records).

Study specific discontinuation criteria are listed below. The FPG and HbA1c values will be measured at the central laboratory.

- 6. Use of (need for) any antihyperglycaemic medication other than investigational product or open-label metformin for more than 14 consecutive days, however insulin during hospitalisation is allowed.
- 7. Treatment with chronic systemic glucocorticoids. However, two temporary periods no longer than 7 days each are allowed.
- 8. Severe and/or frequent hypoglycaemic events, defined as ≥ 1 major event or recurring minor events and the possibility of down-titration and contributing factors (eg, excessive physical activity) has been evaluated.
- 9. Patients whose double blind treatment codes are broken by the investigator.
- 10. Pregnancy.
- 11. FPG >15.0 mmol/L (>270 mg/dL) at Visit 4 (Week 3) confirmed at a repeated measurement.
- 12. FPG >13.3 mmol/L (>240 mg/dL) at Visit 7 (Week 12) and on maximum titrated tolerated dose for at least two weeks confirmed at a repeated measurement.
- 13. FPG >12.2 mmol/L (>220 mg/dL) at Visit 9 (Week 18) and on maximum titrated tolerated dose for at least two weeks confirmed at a repeated measurement.
- 14. FPG >11.1 mmol/L (>200 mg/dL) at Visit 10 (Week 24) confirmed at a repeated measurement.
- 15. HbA1c >8.0% at Visit 11 (Week 30) and Visit 12 (Week 39).
- 16. HbA1c >7.5% at Visit 13 (Week 52), Visit 14 (Week 65) and Visit 15 (Week 78).

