- 17. HbA1c >7.0% at Visit 16 (Week 91).
- 18. Absolute lymphocyte count \leq 400 cells/ μ L confirmed at a repeated measurement, see Appendix D.
- 19. Thrombocyte count <75 000 cells/μL confirmed at a repeated measurement, see Appendix E.

20. Increase in serum creatinine to a level of \geq 133 μ mol /L (\geq 1.5 mg/dL) for men, \geq 124 μ mol/L (\geq 1.4 mg/dL) for women confirmed at a repeated measurement, see Section 3.3.5.2.

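### The Week 24–104 slope comparison in Section 6.4.3 averages individual slopes although HbA1c itself triggers withdrawal; this inflates each arm's slope and costs precision

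*Protocol*

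**What the plan says.** Section 6.4.3 of the protocol sets the Period D durability analysis. On slopes it states: "The same methods used to investigate the slopes of HbA1c after Week 24 in the Period C will be employed"; these methods "will be employed to compare the HbA1c slopes from Week 24 through Period D in the two treatment regimens". The Period C method is in Section 6.2 (durability hypothesis) and Section 6.4.1. It compares mean slopes by Student's t-test, uses observed values only, and admits any patient with a Week 24 HbA1c and one later value. Section 6.4.3 also says: "A summary of the number of patients who maintain desirable HbA1c levels at each time point in Period D will be generated". It gives neither the denominator nor the desirable level. A repeated-measures analysis is mentioned only as an option.

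Section 3.3.5.1 lists these withdrawal criteria:
- criterion 15: "HbA1c >8.0% at Visit 11 (Week 30) and Visit 12 (Week 39"
- criterion 16: "HbA1c >7.5% at Visit 13 (Week 52), Visit 14 (Week 65) and Visit 15 (Week 78"
- criterion 17: "HbA1c >7.0% at Visit 16 (Week 91"

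Unlike the FPG criteria before them, these three mention no confirmatory repeat. Withdrawal covers assessments as well as treatment: "Patients may be discontinued from study treatment and assessments at any time". Section 3.1 applies the rule during Period D, where glycaemic parameters "will be evaluated at Visit 14 to 16 to determine eligibility for discontinuation during the period". The last-observation rule in Section 6.3.4 is written for Week 52 only.

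**The concern.** Whether and when a patient leaves depends on the outcome being analysed. A patient withdrawn at Week 30 contributes a slope from two values six weeks apart, and the second is selected for being high. The t-test gives that slope the same weight as one from eight visits over 80 weeks. The mean slope in an arm is therefore pushed upward, and its variance is dominated by the shortest follow-up.

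The maintenance summary has a related weakness. Under the rule, anyone seen at Week 104 had HbA1c of at most 7.0% at Week 91. A percentage of attending patients would then mostly describe the rule.

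At stake is the long-term efficacy comparison named in the tertiary objective (Section 2.3). The Week 52 primary result is not affected.

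**Working it through.** The plan gives no figure for Period D to reproduce; Section 6.5 sizes the trial for Week 52 only.

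**Inputs from the protocol.** HbA1c visits at Weeks 24, 30, 39, 52, 65, 78, 91 and 104, and the limits of criteria 15–17. Criterion 15 is read as applying at either of its two visits.

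**Assumed inputs.** Week 24 mean 7.0%, between-patient SD 0.85, error SD 0.3, slope SD 0.006 %/week, true mean drift 0.004 %/week. No HbA1c is simulated after the value that triggers withdrawal.

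**Model.** HbA1c of patient i at week t = a_i + b_i(t − 24) + error. Each patient's least-squares slope is taken from the values seen, then averaged; 300,000 patients per setting.

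**Why short follow-up dominates.** The error SD of a slope is 0.3/√Sxx, where Sxx is the sum of squared deviations of the visit weeks.
- All eight visits: Sxx = 5,946, so 0.3/77.1 = 0.0039. With the true slope SD, √(0.006² + 0.0039²) = 0.0072, which agrees with the simulated SD of 0.007 without withdrawal.
- Weeks 24 and 30 only: Sxx = 18, so 0.3/4.24 = 0.071, about 18 times the true drift.
- Weeks 24 to 52 (four visits): Sxx = 444.75, so 0.3/21.1 = 0.014.

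**Mean slope in one arm (true 0.004 %/week).**

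| Rules applied | Mean of individual slopes |
|---|---|
| None | 0.0040 |
| Weeks 52–91 only | 0.0057 |
| Weeks 30/39 only | 0.0089 |
| All | 0.0104 to 0.0105 |

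Under all rules the slope SD is 0.030 against 0.007 without withdrawal, a ratio of 4.3. Moving the Week 24 mean from 6.8% to 7.2% gives mean slopes of 0.0093 to 0.0117. A random intercept-and-slope model fitted by likelihood methods to the same truncated data returns 0.0039 to 0.0040.

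**Between arms.**
- True drifts of 0.004 and 0.008 give mean slopes of 0.0105 and 0.0148: a contrast of 0.0043 against a true 0.004.
- A second set of assumptions (between-patient SD 0.8, slope SD 0.3 %/year, error SD 0.25) gave a contrast of zero for identical arms. With Week 24 means of 7.1% and 6.9% and equal true slopes, a false difference of about 0.05 %/year appeared (0.05/52 ≈ 0.001 %/week), against the arm with the higher Week 24 level.
- Precision, with an assumed 350 patients per arm: SE = SD × √(2/350) = SD × 0.0756. This is 0.00053 without withdrawal and 0.0023 under all rules. A true difference of 0.004 is then 7.6 or 1.8 standard errors.
- In the second set, simulated power for 0.2 %/year was 1.00 with no rule, 1.00 with the Week 52–91 rules only and 0.64 with all rules. The mixed model kept 1.00 throughout.

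**Maintenance below 7.0% at Week 104 (first set).** 37% of patients reach Week 104. Of these 84% are below 7.0%, and 0.37 × 0.84 = 0.31 of all patients. Without withdrawal it would be 38% of all. Doubling the drift to 0.008 moves the attending-patient figure only from 84% to about 78%, while the all-patient figure falls from 31% to 22%.

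**The case against.** A reader might infer that the whole set of 104-week efficacy results is produced by the withdrawal rule. The documents do not support that, and several objections stand.

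- Section 6.4.3 speaks of a number of patients. A count over all patients responds sensibly: 31% against 38% without withdrawal, falling to 22% when drift doubles. Near-certain maintenance arises only if attending patients become the denominator, which the text neither says nor rules out. An SAP could settle that.
- The tightening limits of Period D are not the main source of slope distortion. The 8.0% limit at Weeks 30 and 39, a Period C rule, accounts for most of it.
- The harm is not chiefly a biased comparison. With equal Week 24 levels, both arms shift by nearly the same amount.
- A slope among completers (0.0013 in the simulation) is not planned, so it cannot be held against the plan.
- Section 3.3.5.2 asks for end-of-period procedures at withdrawal. These may add one HbA1c near the triggering value and soften the two-point slopes. Reading criterion 15 as requiring both visits would also soften the effect.
- The analysis is called supplemental (Section 6.6) and lies outside the fixed-sequence test.

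The slope method remains open to criticism. It is stated rather than left to the SAP, and the more suitable model is only optional.

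**Conclusion.** The point holds in a limited form. The planned average of individual slopes does not estimate the drift in either arm: about 0.010 against a true 0.004 %/week under the stated assumptions. A roughly fourfold slope SD makes the between-arm test much less precise than the data allow. Bias in the contrast is small and arises when the arms differ in Week 24 level. The maintenance summary is sound as a count over all patients and misleading as a percentage of those attending.

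The sizes rest on assumed HbA1c distributions that the protocol does not give. Across the ranges tried, each arm's slope was always inflated: 0.26 to 0.78 %/year for a true 0.20 under all rules, and 0.22 to 0.33 under the Week 52–91 rules alone. Since the 104-week analysis is supplemental, the priority is modest.

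**What to change.** Change Section 6.4.3, and carry the change into the SAP before the Week 104 data are unblinded:

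1. Make a likelihood-based repeated-measures model with random intercept and slope, using every observed HbA1c from Week 24 on, the planned Week 24–104 slope comparison in place of the t-test on individual slopes. Because the value that triggers withdrawal is itself in the data, such a model can allow for withdrawal under criteria 15–17.
2. Report the per-visit maintenance summary over all treated randomized patients. Count a patient withdrawn under criteria 15–17 as not maintained from then on, and state how other withdrawals are counted.

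A time-to-first-exceedance analysis against each visit's limit is not advised. The limits fall from 8.0% to 7.0%, so a patient stable at 7.3% would fail at Week 91 without any drift.

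The cost is some wording and a few tables. No withdrawal criterion or visit changes. Reported maintenance rates will be lower than among attending patients, and the slope result will rely on the mixed model's assumptions: a linear course, a correct variance structure, and other withdrawals explained by the observed data.

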6.4.4 Safety measurements and variables

Descriptive statistics will be provided for the safety laboratory variables. AEs will be tabulated. Other safety-related variables, such as pulse, physical examination and ECG tests, will be summarised with descriptive statistics, tabulations and/or listings.

6.5 Determination of sample size

With a total of 838 patients randomized and treated (or 419 per treatment group), there is 95% power to establish the non-inferiority comparison on change from baseline to Week 52 in HbA1c at the 5% level assuming standard deviation of change from baseline in HbA1c is 1.1%, with a non-inferiority limit set at 0.35% and a zero true difference between the two randomized treatments. The sample size also assumes about 35% of the randomized patients will be excluded from the per protocol analyses set.

For the non-inferiority primary efficacy endpoint, non-inferiority is defined as the upper limit of the two-sided 95% confidence interval of the difference in change in HbA1c from baseline to Week 52 between saxagliptin plus metformin and glipizide plus metformin to be less than 0.35%, where a change of 0.35% or more is considered a clinically relevant difference.

6.6 Interim analyses

Not applicable. The study will declare data base lock after 52 weeks of randomized treatment for the primary analysis. Subsequent analyses for additional data after 104 weeks of randomized therapy is supplemental.

6.7 Data monitoring committee

A Data Monitoring Committee (DMC) will be reviewing safety data on a periodic basis, including the incidence of AEs, laboratory measurements and safety assessments to ensure the ongoing safety of study patients. An independent statistician will be contracted to provide the DMC with essential safety data during the study. The DMC responsibilities, authorities, and procedures will be documented in a DMC charter. The personnel involved in the clinical study at AstraZeneca and at Bristol-Myers Squibb will remain blinded to these analyses and will have no knowledge of the results presented to the DMC.

7. STUDY MANAGEMENT

7.1 Monitoring

Before first patient into the study, a representative of AstraZeneca will visit the investigational study centre to:

- Determine the adequacy of the facilities.
- Discuss with the investigator(s) (and other personnel involved with the study) their responsibilities with regard to protocol adherence, and the responsibilities of AstraZeneca or its representatives. This will be documented in a Clinical Study Agreement (CSA) between AstraZeneca and the investigator.
- Discuss the specific requirements of the genetic research with the investigator(s) (and other personnel involved with the study).

During the study, a monitor from AstraZeneca or company representing AstraZeneca will have regular contacts with the study centre, including visits to:

- Provide information and support to the investigator(s).
- Confirm that facilities remain acceptable.
- Confirm that the investigational team is adhering to the protocol that data are being accurately recorded in the eCRFs, and that investigational product accountability checks are being performed.
- Perform source data verification (a comparison of the data in the eCRFs with the patient's medical records at the hospital or practice, and other records relevant to

Clinical Study Protocol Drug Substance Saxagliptin Study Code D1680C00001 Date

the study). This will require direct access to all original records for each patient (eg, clinic charts).

• Perform source verification of the genetic consent of participating patients and ensure that the investigational team is adhering to the specific requirements of this genetic research.

The monitor or another AstraZeneca representative will be available between visits if the investigator(s) or other staff at the centre needs information and advice.

7.2 Audits and inspections

Authorised representatives of AstraZeneca, a regulatory authority, or an Ethics Committee may visit the centre to perform audits or inspections, including source data verification. The purpose of an AstraZeneca audit or inspection is to systematically and independently examine all study-related activities and documents to determine whether these activities were conducted, and data were recorded, analysed, and accurately reported according to the protocol, Good Clinical Practice (GCP), guidelines of the International Conference on Harmonisation (ICH), and any applicable regulatory requirements. The investigator should contact AstraZeneca immediately if contacted by a regulatory agency about an inspection at his or her centre.

7.3 Training of staff

The principal investigator will maintain a record of all individuals involved in the study (medical, nursing and other staff). He or she will ensure that appropriate training relevant to the study is given to all of these staff, and that any new information of relevance to the performance of this study is forwarded to the staff involved.

Before the first patient is entered into the study, the investigational staff will be trained to use the WBDC system by a web-based learning (ie, self-study) method.

7.4 Changes to the protocol

Study procedures will not be changed without the mutual agreement of the Co-ordinating Investigator (if applicable), AstraZeneca, and Bristol-Myers Squibb.

If it is necessary for the Clinical Study Protocol to be amended, the amendment and/or a new version of the Clinical Study Protocol (Amended Protocol) must be notified to or approved by each Ethics Committee, and if applicable, also the local regulatory authority, before implementation. Local requirements must be followed.

If an administrative change is required, such a change must be notified to or approved by each Ethics Committee according to local requirements.

If a protocol amendment requires a change to a particular centre's Informed Consent Form, then AstraZeneca and the site's Ethics Committee must be notified. Approval of the revised

Clinical Study Protocol Drug Substance Saxagliptin Study Code D1680C00001 Date

Informed Consent Form by AstraZeneca and by the Ethics Committee is required before the revised form is used.

AstraZeneca will distribute amendments and new versions of the protocol to each principal investigator(s), who in turn is responsible for the distribution of these documents to his or her Ethics Committee, and to the staff at his or her site. The distribution of these documents to the regulatory authority will be handled according to local practice.

7.5 Study agreements

The principal investigator at each site must comply with all the terms, conditions, and obligations of the CSA for this study. In the event of any inconsistency between this Clinical Study Protocol and the CSA, the Clinical Study Protocol shall prevail.

7.6 Study timetable and end of study

Before a patient's enrolment in the study and any study-related procedures are undertaken, the following should be fulfilled:

- Signed Clinical Study Protocol and other agreements between AstraZeneca and the Principal Investigator/Study Site.
- Approval of the study by the Ethics Committee.
- Approval of the study, if applicable, by the regulatory authority.

The planned overall timetable for the study is as follows:

First Patient In O4 2007 - O1 2008

Last Patient In Q3 2008

For 52 weeks randomized treatment:

Last Patient Last Visit O3 2009

Data base lock Q4 2009

For 104 weeks randomized treatment:

Last Patient Last Visit Q3 2010

Data base lock Q4 2010

End of study is defined as database lock, which is the time point after which no patients will be exposed to study related activities.

8. ETHICS

8.1 Ethics review

AstraZeneca will provide Ethics Committees and Principal Investigators with safety updates/reports according to local requirements.

The final Clinical Study Protocol, including the final version of the Informed Consent Form, must be approved or given a favourable opinion in writing by an Ethics Committee as appropriate. The investigator must submit written approval to AstraZeneca before he or she can enrol any patient into the study.

The Principal Investigator is responsible for informing the Ethics Committee of any amendment to the protocol in accordance with local requirements. In addition, the Ethics Committee must approve all advertising used to recruit patients for the study. The protocol must be re-approved by the Ethics Committee annually, as local regulations require.

Progress reports and notifications of serious and unexpected adverse drug reactions will be provided to the Ethics Committee according to local regulations and guidelines.

8.2 Ethical conduct of the study

The study will be performed in accordance with ethical principles that have their origin in the Declaration of Helsinki and are consistent with ICH/GCP, applicable regulatory requirements and the AstraZeneca policy on Bioethics.

For studies including genetic analysis special precautions are taken as described in Section 4.9.

